**Characterisation of Tissue Stiffness to Improve the Diagnosis and
Management of Uterine Fibroids**

University of Ottawa
NCT #: NCT03369600
December 6, 2017

Characterization of tissue stiffness to improve the diagnosis and management of uterine fibroids

Principal Investigator: [name], FRCSC

Co-investigators: [name], MD, FRCSC

[name], BSc, MSc, PhD

[name], PEng

[name]

[name] Candidate

Background:

Uterine fibroids are the most common gynecological tumors, with a prevalence up to 70% in premenopausal women^{1,2}. Although these tumors are benign, 20% – 50% of women with uterine fibroids are symptomatic¹ and morbidities are significant, including menstrual abnormalities (e.g. heavy and prolonged bleeding leading to iron deficiency anemia), bulk symptoms (e.g. pelvic pain, bowel and bladder obstructions, abdominal protrusion), and infertility¹⁻⁵. Symptomatic fibroids can negatively impact women's quality of life and results in loss of productivity^{6,7}. The management of uterine fibroids is estimated to cost the healthcare system between \$2200 and \$15,952 per patient, per year⁸.

Uterine fibroids are globular masses composed of disordered myometrial cells contained within abundant extracellular matrix^{9,10}. Fibroids degenerate as they outgrow their blood supply¹¹, and can take on a range of characteristics while presenting on a spectrum of very soft to extremely hard masses^{4,11-13}. Fibroid degeneration state is currently not considered in diagnosis, management or surgical planning. Instead, fibroids are classified based only on their location¹⁴ and are described by their size and shape.

While medical management is advancing^{5,10,12,15} surgical removal through myomectomy or hysterectomy is the current standard of care for uterine fibroids⁵. Myomectomy can spare the uterus to preserve fertility, yet complications occur in 2-35% of cases¹⁶⁻¹⁸. Fibroid mechanical properties appear to be relevant to surgical outcome: our surgeons at TOH report *very hard* or

Based on findings by ^{19,20}, a sample size of 30 in each group was deemed appropriate to detect effect size of at least 12kPa with 90% power at a significance level of $\alpha=0.05$. Due to the prospective design, we will not know the distribution of fibroid types a priori. A power analysis to confirm final sample size will be conducted with preliminary data collected from our first 15 participants in each group FIB participants and 15 CON participants.

Recruitment: Prospective FIB participants will be recruited from a list of patients consented for myomectomy or hysterectomy due to uterine fibroids at The Ottawa Hospital – General Campus. Potential participants that have provided “permission to contact” by research as indicated on the institution’s electronic medical record (EMR) or the OBIEE dashboard will be contacted by the study’s research coordinator or research assistant. If “permission to contact” is not specified then only patients of our participating gynecologists will be recruited. In these cases, the participating gynecologist will contact the patient to introduce the study themselves, and if agreed, the study’s research coordinator or research assistant will contact them to discuss the study further. Initial contact will be made through telephone (see attached telephone script). If they agree to participate, then ultrasound imaging session(s) will be booked within one week of their surgery.

CON participants will be recruited from the community. Advertisement posters will be placed around The Ottawa Hospital and the University of Ottawa. Individuals interested in participating will contact the research coordinator by phone or email. Potential CON participants will be screened for eligibility and if they agree to participate then experimental session(s) will be booked at their convenience.

At the time of the ultrasound imaging session, a consent form containing further information about the purpose of the study, risks and benefits will be provided. Participants will be allotted as much time as they would like to review the form and ask the researchers any questions/concerns they may have. At time of study introduction, we will offer to send a full consent form prior to ultrasound imaging session so they can review the form at their

convenience. Signed consent will be obtained onsite by the research coordinator or research assistant before data collection commences.

Data Collection:

Ultrasound Imaging: All participants will attend two ultrasound imaging sessions at the Motor Function and Movement Laboratory at the University of Ottawa. The sessions for the FIB participants will occur within 1 month of their planned surgery. Each session will take approximately 1 hour to complete. After providing signed informed consent, participants will complete a set of validated questionnaires about their gynecological and medical history, symptoms, and quality of life as it relates to uterine fibroids. The questionnaires include the Medical Outcomes Study 36 Item Short Form Survey²¹, the Uterine Fibroids Symptoms Quality of Life questionnaire²², and the Menstrual Bleeding Questionnaire²³.

All participants will then undergo 2D and 3D ultrasound scans with a GE ultrasound system (Voluson S6, General Electric, Boston, MA) as well as a SWE transvaginal ultrasound scan using an Aixplorer ultrasound system (Supersonic Ultrafast™ Aixplorer®, Apexium Medical, Canada). SWE and volume measurements of their uterus as a whole, at 10 healthy sites and at all relevant fibroid sites deemed will be recorded. Morphologic measurements of the selected fibroids will be made and fibroids will be given identification numbers. SWE will be used to determine tissue stiffness (kPa) at 10 healthy sites and at each fibroid. Three repetitions of each measurement will be performed to satisfy Primary Objective 2. The second ultrasound imaging session will occur within one week where the imaging protocol will be repeated. This second data collection will be to evaluate reliability (Primary Objective 2).

The rest of the data collection protocol applies to FIB participants only.

Surgical Intervention: The surgical approach (myomectomy or hysterectomy + abdominal or laparoscopic) will be recorded as well as secondary outcomes including operating time, blood loss, surgical technique conversions, failed/incomplete excisions, and additional procedures performed. These data will be used for descriptive purposes.

Tissue Sampling: Consistent with TOH protocol, all uterine tissue will be sent to pathology for evaluation. For patients who receive a hysterectomy, a pathologist will surgically excise five ≥ 1 cm³ samples of healthy uterine tissue from the sites identified using US and each fibroid will be dissected out. All fibroids will be labelled with their respective identification number, measured, weighed, and then transported to [name] laboratory at the Ottawa Heart Institute for mechanical testing.

Mechanical Testing: The healthy tissue samples will be cut to size while the fibroids will be tested intact. All samples will be loaded into a set of 3D printed clamps attached to a biaxial tissue testing device (Biotester, CellScale, Waterloo, Canada) and tested at body temperature, cyclically in compression (1 Hz, 6% pre-compression). Relevant material properties will be calculated, including the complex modulus of elasticity, loss factor, and stiffness contrast ratio. All samples will be returned to pathology. Pathology charts will be retrospectively reviewed to extract descriptive fibroid characteristics.

Statistical Analysis Plan: All data will be tested for normality and non-parametric equivalent tests will be used as appropriate. Validation of stiffness measures derived from SWE will be done through linear regressions (Primary Objective 1) which will be performed for the healthy and fibroid tissues separately and combined to map the relationship between SWE outcomes and the results of ex-vivo mechanical testing.

For the reliability analysis (Primary Objective 2), ANOVA's will test for differences between measures taken across multiple sessions and visits to investigate site-specific differences in stiffness measures. Intra-class correlation coefficients (ICCs) will be determined for measurements within session, between-session, and between-site.

Factorial ANOVAs will evaluate site- and group (CON vs FIB) differences in uterine tissue stiffness measured with SWE. ANOVAs will also investigate differences in SWE stiffness measures between healthy tissue, normal fibroids and degenerative fibroids (Primary Objective 3). Appropriate post-hoc comparisons will be performed, and post-hoc power analyses will evaluate the effect sizes for non-significant differences.

Significant differences in 2D, 3D ultrasound, and ex-vivo volume estimates will be determined with dependent T-tests at the $p < 0.05$ level (Secondary Objective 1). The standard error of measurement (SEM) will also be computed for 2D and 3D ultrasound volume measures, using ex-vivo morphology and volume measurements as a reference.

Clinical significance of project: Establishing SWE methods for uterine fibroid characterization would result in a ground-breaking advance for directing medical and surgical decision-making in this highly prevalent gynaecological condition. Magnetic resonance (MRI) and ultrasound (US) imaging are the current standards of care for evaluating uterine fibroids. They inform about number, size and location of fibroids, but are not capable of characterising the degeneration state of a given fibroid. Fibroid degeneration state has huge implications for determining the potential for and progress of medical management, and for selecting the best surgical approach. The degeneration state of a fibroid can drastically alter its material properties including stiffness, a characteristic that can be measured using SWE. Thus, SWE could provide the missing and necessary information on fibroid degeneration state to inform treatment decisions. Findings from this study has the potential to revolutionize the management of uterine fibroids, leading to more timely diagnoses, reduced surgical time and complications, better inform decisions for medical therapies and, ultimately, safer, more effective, and less costly care.

References:

1. Okolo, S. Incidence, aetiology and epidemiology of uterine fibroids. *Best Pract. Res. Clin. Obstet. Gynaecol.* **22**, 571–588 (2008).
2. Catherino, W. H., Parrott, E. & Segars, J. Proceedings from the National Institute of Child Health and Human Development Conference on the Uterine Fibroid Research Update Workshop. *Fertil. Steril.* **95**, 9–12 (2011).
4. Bulun, S. E. Uterine Fibroids. *N. Engl. J. Med.* **369**, 1344–1355 (2013).
5. Stewart, E. A. Uterine Fibroids. *N. Engl. J. Med.* **372**, 1646–1655 (2015).

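### For the Objective 1 regressions and the SWE stiffness ANOVAs the SAP states no unit of analysis and no woman-level term; run on site or specimen rows, error rates and intervals are wrong if readings correlate within a woman.

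*Combined protocol and SAP*

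**What the plan says.** Under Data Collection, Ultrasound Imaging, all participants are scanned: "SWE will be used to determine tissue stiffness (kPa) at 10 healthy sites and at each fibroid". Three repetitions are taken in each of two sessions. Under Tissue Sampling, each hysterectomy patient gives five "samples of healthy uterine tissue from the sites identified using US and each fibroid will be dissected out". Controls give SWE sites only, because the tissue steps apply to FIB participants.

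The Statistical Analysis Plan then names three analyses of these data:

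- Objective 1: "linear regressions (Primary Objective 1) which will be performed for the healthy and fibroid tissues separately and combined".
- Group and site: "Factorial ANOVAs will evaluate site- and group (CON vs FIB) differences in uterine tissue stiffness measured with SWE".
- Tissue state: "ANOVAs will also investigate differences in SWE stiffness measures between healthy tissue, normal fibroids and degenerative fibroids". The Objective 3 label follows this sentence, not the group-and-site one.

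None of the three states what one row is, whether values are averaged per woman, or whether woman enters the model. Dependence is recognised elsewhere. For reliability (Objective 2), "Intra-class correlation coefficients (ICCs) will be determined for measurements within session, between-session, and between-site". For the secondary volume objective, "ex-vivo volume estimates will be determined with dependent T-tests". The sample size, 30 per group, is counted in women.

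**The concern.** Sites, fibroids and specimens from one woman share her age, hormonal state, anatomy and scanning conditions, so their stiffness values may well be correlated. A test that ignores this uses the wrong error term. Comparisons between women then look more precise than they are, and comparisons within women look less precise.

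The stake is twofold. An unstated unit can be settled after the data are seen, and the choice can change the result. If rows are used, the study could report CON-FIB differences too often, miss site differences, and give the slope of modulus on SWE more precision than it has. The stated research goal is a classification to guide management, so these results matter.

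**Working it through.** **Inputs.** From the documents: 30 women per group, 10 healthy sites per woman, five healthy specimens per hysterectomy patient, alpha 0.05. Assumed, because the documents give none: within-woman ICC of 0.1, 0.3 and 0.5, total variance 1, one value per site (repetitions and sessions averaged). All error rates are under the null.

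**The plan's own figure.** The 30 per group for 12 kPa at 90% power cannot be reproduced, because no SD is stated. It is consistent with an SD of about 14.3 kPa: 2 × (1.960 + 1.282)² × 14.3² / 12² = 29.8, so 30 women. It does not say how 10 readings per woman enter the test.

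**1. CON-FIB on 10 rows per woman, no woman term.** The variance of a group mean is larger than the test assumes by the design effect DE = 1 + (10 − 1) × ICC. True type I error ≈ 2 × [1 − Φ(1.96/√DE)].

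| ICC | DE | 1.96/√DE | Formula | Simulated (10,000 runs) |
|---|---|---|---|---|
| 0 | 1.0 | 1.960 | 5.0% | – |
| 0.1 | 1.9 | 1.422 | 15.5% | 15.3% |
| 0.3 | 3.7 | 1.019 | 30.8% | 31.2% |
| 0.5 | 5.5 | 0.836 | 40.3% | 40.1% |

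**2. Site and group-by-site on the same rows.** The error mean square estimates the total variance, 1, but site contrasts vary only by 1 − ICC, so F is shrunk by that factor. With 9 numerator df, type I error ≈ P(χ²₉ > 16.92/(1 − ICC)).

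| ICC | 16.92/(1 − ICC) | Formula | Simulated, site | Simulated, group-by-site |
|---|---|---|---|---|
| 0.1 | 18.80 | 2.7% | 2.4% | 2.7% |
| 0.3 | 24.17 | 0.4% | 0.4% | 0.4% |
| 0.5 | 33.84 | 0.01% | 0.03% | 0.02% |

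**3. Objective 1 regression, five specimens per woman.** The slope variance is understated by about 1 + (5 − 1) × ICC(SWE) × ICC(residual). Coverage of a nominal 95% interval ≈ 2Φ(1.96/√factor) − 1.

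| ICC of SWE | ICC of residual | Factor | Coverage |
|---|---|---|---|
| 0.1 | 0.1 | 1.04 | 94.5% |
| 0.3 | 0.3 | 1.36 | 90.7% |
| 0.5 | 0.5 | 2.00 | 83.4% |
| 0.3 | 0.1 | 1.12 | 93.6% |
| 0.5 | 0.1 | 1.20 | 92.6% |
| 0.5 | 0 | 1.00 | 95.0% |

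Simulation of the first three rows (no true link, 10 to 30 women) gives rejection of about 6%, 9% and 16–17%, hence coverage of about 94%, 91% and 83–84%. The last three rows show that the effect fades if SWE accounts for the differences between women.

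**4. Three-class ANOVA.** If most women contribute to every class, the comparison is largely within women and a row-level test is too conservative. If a woman's fibroids tend to share a state, or CON sites are pooled into healthy tissue, it becomes partly between women and can be too liberal. The SAP settles neither point, so no figure is given.

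**5. Does the remedy work?** With one mean per woman, the simulated CON-FIB type I error is 4.8–5.5% for ICC 0 to 0.5. A split-plot ANOVA gives 4.7–5.1% for all three tests when every pair of sites is equally correlated. When correlation decays across sites (AR(1), 0.5 to 0.8), CON-FIB stays near 5%, but the uncorrected site and group-by-site tests rise to about 8–11%. A random woman intercept brings the five-specimen regression to 5.0–6.4% rejection.

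**The case against.** The strongest reply is that this is brevity, not error. The sample size counts women, pairing is recognised for volumes, and between-site ICCs are planned, so the authors may well intend a repeated-measures ANOVA. On that reading the CON-FIB test is valid, and the largest figures above concern the analysis with the best benign reading. This stands as far as it goes. It does not reach the Objective 1 regressions, where no repeated-measures meaning is implied. Nor does it readily fit the three-class ANOVA: the sample-size paragraph says that the mix of fibroid types is unknown in advance, so some women may lack a class.

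It is also fair that the Objective 1 effect is small at ICC 0.1 and depends on residual correlation. The SAP sets no significance criterion for validation, so the harm there is to the interval.

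A reader might infer more than the documents support:

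- That the SAP instructs row-level analysis. It is silent.
- That every woman gives fibroids and specimens. Controls give sites only, the five healthy specimens are specified only for hysterectomy patients, and a FIB woman may have a single fibroid.
- That the CON-FIB ANOVA is explicitly the Objective 3 test. The label follows the three-class sentence.
- That 15–40% is this study's error rate. It is conditional on an assumed ICC and on row-level analysis.

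**Conclusion.** The omission is certain; its size is not. The SAP leaves the unit of analysis open for Objective 1 and for both stiffness ANOVAs, although the data are clustered by design. If rows were treated as independent and readings correlate within women, then at ICC 0.1, 0.3 and 0.5:

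- the CON-FIB type I error would be about 15%, 31% and 40%;
- the site and group-by-site tests would fall below 3% at ICC 0.1 and below 0.5% from ICC 0.3;
- the Objective 1 interval would cover about 94%, 91% and 83–84%, assuming five specimens per woman, the same ICC on both scales and no true link.

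The three-class ANOVA could err in either direction, and a claim that it is simply too liberal would not be supported. At ICC 0 there is no distortion. The point should be fixed before analysis; it does not make the study unsound.

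**What to change.** Amend the Statistical Analysis Plan as follows:

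- **Unit.** State the unit of analysis for each of the three analyses, and how repetitions and sessions are combined.
- **CON-FIB.** Test on one mean per woman, or in a mixed model with a random woman intercept.
- **Site and group-by-site.** Use a repeated-measures analysis with a sphericity correction such as Greenhouse-Geisser, or an unstructured or robust covariance. A random intercept alone assumes equal correlation between sites, which cannot be taken for granted. An unstructured matrix for 10 sites has 10 × 11 / 2 = 55 parameters against 60 women, so the corrected ANOVA is the lighter choice.
- **Objective 1 and the three-class comparison.** Use a random woman effect or woman-clustered standard errors, with a small-sample correction given the number of women. State whether CON sites count as healthy tissue.

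The cost is SAP wording and slightly more analysis in standard software, with no new data. The downside is that p-values for comparisons between women will be less favourable than on rows.

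### The Primary Objective 3 ANOVA of three tissue classes relies on a common variance that the plan neither justifies nor relaxes; a mixed model with class-specific variances would remove the dependence cheaply

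*Combined protocol and SAP*

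**What the plan says.** The Statistical Analysis Plan section covers the three-class comparison in one sentence: "ANOVAs will also investigate differences in SWE stiffness measures between healthy tissue, normal fibroids and degenerative fibroids (Primary Objective 3". The next sentence adds "Appropriate post-hoc comparisons will be performed", without naming a procedure. The only stated assumption check opens the section: "All data will be tested for normality and non-parametric equivalent tests will be used as appropriate". Equal variances, Welch's test and class-specific variances are not mentioned.

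Three other places bear on whether a common variance is a safe assumption:

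- The Background describes fibroids "presenting on a spectrum of very soft to extremely hard masses", and the section on clinical significance says "The degeneration state of a fibroid can drastically alter its material properties including stiffness".
- Data Collection, Ultrasound Imaging, fixes the healthy sampling but not the number of fibroids: "SWE will be used to determine tissue stiffness (kPa) at 10 healthy sites and at each fibroid".
- The sample-size paragraph under Methodology concedes "Due to the prospective design, we will not know the distribution of fibroid types a priori".

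**The concern.** The ordinary F test divides the between-class mean square by one pooled within-class variance. If a class is both smaller and more variable than the others, the pooled variance is dominated by the large, quiet class and understates the error in the small class's mean. The test then rejects too often when the means are equal. If the variable class is the larger one, the error can run the other way.

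Healthy tissue comes from every woman, at 10 sites each. Fibroids come only from the FIB women and are then split into two types. The unfavourable pattern is therefore plausible, and a check of normality would not detect it. At stake is whether a significant Objective 3 result shows a difference in mean stiffness between tissue states or partly reflects a difference in spread. The contrast between the two fibroid types matters most, because the project's rationale rests on recognising degeneration.

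**Working it through.** **The plan's own figure.** The sample-size paragraph says "a sample size of 30 in each group was deemed appropriate to detect effect size of at least 12kPa with 90% power", at α = 0.05, and gives no SD. It can only be solved backwards. From n = 2(z₀.₉₇₅ + z₀.₉₀)²σ²/δ², σ = 12 × √(30/2) / (1.960 + 1.282) ≈ 14.3 kPa (two-sided, normal approximation). This is one common SD for FIB against CON and says nothing about spread within the three tissue classes.

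**Why size and spread interact.** Under equal means, the expected numerator of F is Σ(1 − nᵢ/N)σᵢ² / 2, and the expected denominator is Σ(nᵢ − 1)σᵢ² / (N − 3). SDs and counts below are assumptions, in the order healthy/normal/degenerative.

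- n = 60/25/12, SD 8/16/24: numerator (24.4 + 190.0 + 504.7)/2 = 359.6; denominator (3776 + 6144 + 6336)/94 = 172.9; ratio 2.08.
- n = 30/30/30, same SDs: numerator (2/3)(64 + 256 + 576)/2 = 298.7; denominator 896/3 = 298.7; ratio 1.00.
- n = 30/60/40, SD 8/12/12: numerator (49.2 + 77.5 + 99.7)/2 = 113.2; denominator (1856 + 8496 + 5616)/127 = 125.7; ratio 0.90.

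A ratio above 1 means too many rejections, and a ratio below 1 too few.

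**Pairwise contrast, first case.** The true SE of normal minus degenerative is √(256/25 + 576/12) = 7.63. The pooled SE is √(172.9 × (1/25 + 1/12)) = 4.62, a ratio of 0.605. A nominal 95% interval then covers about P(|Z| < 1.986 × 0.605) = 77%; simulation gives 76%.

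**Simulation.** 40,000 runs per row, equal means, independent normal values, nominal 5%. Intervals are unadjusted pooled-variance 95% intervals. Each cell gives results for SDs 8/12/12, 8/12/16 and 8/16/24 in turn.

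| n | Pooled F rejects (%) | Coverage, normal v degenerative (%) | Coverage, healthy v normal (%) |
|---|---|---|---|
| 60/25/12 | 11, 16, 23 | 88, 83, 76 | 92, 94, 93 |
| 60/40/20 | 8, 12, 15–16 | 90, 86, 81 | 94, 96, 97 |
| 30/20/10 | 8, 12, 16 | 90, 86, 81 | 94, 96, 96 |
| 30/15/15 | 8, 10, 12 | 90, 89, 86 | 94, 96, 96 |
| 30/30/30 | 5, 6, 6 | 92, 92, 90 | 96, 98, 99 |
| 30/60/40 | 4, 5, 6 | 93, 91, 90 | 98, 99, >99 |
| 60/80/40 | 5, 8, 9 | 92, 89, 86 | 97, 98, 99 |

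With equal SDs every F rate is 5%. Welch's ANOVA stays at about 5% in all rows.

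**Outside this grid.**
- If only degenerative fibroids are more variable (SD ratio 1:1:3), 60/80/40 gives 14%.
- If healthy tissue has the larger SD (2:1:1), 60/20/10 gives 0.5%, so the test is very conservative.

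**The fallback.** Kruskal-Wallis also responds to unequal spread. It rejects about 10% (SD 8/12/16) and 13–14% (8/16/24) at 60/25/12, and about 9.5% at 30/15/15 with SD ratio 1:2:2.

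**Is Welch enough?** It needs independent values. Take equal SDs, an assumed within-woman correlation of 0.5, 60 women with 10 healthy sites each and 30 women with 2 fibroids each. Row-level Welch then rejects anywhere from about 2% to 17%. The rate depends on whether a woman's effect is shared between her healthy and fibroid tissue, and on how fibroid types fall within and between women. Its error rate is therefore not controlled here.

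**The case against.** A reader might infer that the protocol says fibroid stiffness is more spread than healthy stiffness, that fibroids are the small classes, and hence that the Objective 3 p-values and post-hoc intervals are anti-conservative. The documents do not support that chain.

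- They give no within-class SD and say nothing about the spread of healthy tissue. The range in the Background is for all fibroids together. Since degeneration is said to change stiffness, part of that range may be a difference between the two fibroid classes, which is the mean difference the ANOVA is meant to detect.
- The type split is declared unknown and fibroids per woman are not stated. Nor does the plan say whether healthy tissue in this comparison comes from all 60 women or only the 30 FIB women. With 30/30/30 or 30/60/40 the F test runs at about 4–6%.
- No post-hoc method or interval is named, the word appropriate does not exclude an unequal-variance procedure, and some pooled healthy v normal intervals would be too wide.
- The most alarming rates, 32% and 49% at n = 600/40/20 (SDs 8/12/16 and 8/16/24), need every healthy site to be an independent row. Sites within a woman are not independent, so those rates do not describe a sound analysis.

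All of this stands, and it makes the direction and size of the error conditional. It does not remove the gap. The plan names ANOVA without qualification, checks only normality, and falls back on a test that unequal spread also disturbs. Even with balanced classes, where the F test is near nominal, pooled normal v degenerative intervals in these scenarios cover 90–92%.

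**Conclusion.** The point holds as a conditional weakness in specification. Objective 3 is left dependent on a common variance that the protocol gives reason to doubt and does not examine. If fibroids are more variable than healthy tissue within the assumed SD range, type I error is about 8–23% when each fibroid class is smaller than the healthy class, and about 4–9% when at least one is as large or larger. Pooled normal v degenerative intervals, if used, would cover about 76–93%.

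These figures assume normal, independent values, with SDs and counts that the documents do not supply. They show the sensitivity and do not forecast this study's error rate. Because those inputs are unknown, a method that does not need them is the better choice.

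**What to change.** For Primary Objective 3, replace the ANOVA wording with a linear mixed model for SWE stiffness. It should have tissue class as a fixed effect, a random effect for woman, a separate residual variance for each tissue class, and Satterthwaite or Kenward-Roger degrees of freedom. Take the pairwise contrasts, with intervals, from that model.

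State whether CON women's healthy tissue is included. State also how the three repetitions and two sessions enter, for example as one average per site or fibroid, so that the residual variance refers to sites and fibroids.

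Do not make the choice depend on a preliminary variance test, and do not use Kruskal-Wallis as the remedy for unequal spread. Welch's ANOVA with Games-Howell contrasts is suitable only if the values analysed are independent within and across classes. One mean per woman per class does not achieve that, because FIB women supply both healthy and fibroid tissue.

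The cost is SAP wording, slightly more analysis work, and software that fits class-specific residual variances. If variances are in fact equal, some power is lost: 88% to 85% for Welch's test in one simulated case. The mixed model itself was not simulated.

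### Non-significant Primary Objective 3 differences are to be read through post-hoc power with no confidence interval planned, so the plan does not set out to show which stiffness differences the data exclude

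*Combined protocol and SAP*

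**What the plan says.** The Primary Objective 3 paragraph of the Statistical Analysis Plan sets out two families of test. First, "Factorial ANOVAs will evaluate site- and group (CON vs FIB) differences in uterine tissue stiffness measured with SWE". Second, "ANOVAs will also investigate differences in SWE stiffness measures between healthy tissue, normal fibroids and degenerative fibroids". Post-hoc comparisons follow, with no multiplicity method named, and then the clause at issue: "post-hoc power analyses will evaluate the effect sizes for non-significant differences". The section opens with a general rule: "All data will be tested for normality and non-parametric equivalent tests will be used as appropriate".

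No confidence interval, equivalence margin or other interval estimate is named for any objective. The only precision-type quantities are the intra-class correlations (Primary Objective 2) and the standard error of measurement for ultrasound volumes (Secondary Objective 1). Neither applies to the Objective 3 contrasts.

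The sample-size paragraph under Participants gives the design difference: "a sample size of 30 in each group was deemed appropriate to detect effect size of at least 12kPa with 90% power", at α = 0.05. It states no SD and no sidedness. It adds: "Due to the prospective design, we will not know the distribution of fibroid types a priori".

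**The concern.** Objective 3 asks whether SWE stiffness separates healthy tissue from the different states of fibroid. After a non-significant contrast, the useful question is whether the data rule out a relevant stiffness difference or are too imprecise to say. The first answer would count against SWE as a discriminator for that pair of tissues. The second would call for more data. Because the mix of fibroid types is unknown in advance, a small subgroup with an imprecise contrast is a realistic prospect.

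Post-hoc power is the only tool the plan names for this, and it does not answer the question. An estimate with a confidence interval does.

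**Working it through.** **Inputs.** From the sample-size paragraph: 30 per group, 12 kPa, 90% power, α = 0.05. Assumed, because the documents do not state them: the SD, a two-sided test, no multiplicity adjustment, and one independent value per woman.

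**1. The plan's own figure.** Without an SD, 30 per group cannot be reproduced. It can only be solved backwards. With the noncentral t distribution, 30 v 30 at 90% power needs a standardised difference of 0.8512 (two-sided), so the SD is 12 / 0.8512 = 14.1 kPa. A one-sided test implies 15.7 kPa. Both are assumptions, not figures from the plan.

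**2. Power at the observed effect.** For a two-group contrast with ν degrees of freedom, p fixes |t| = t(1 − p/2, ν). Observed power is P(|T| > t(0.975, ν)), where T is noncentral t with noncentrality |t|. The SD does not enter. With ν = 58 the critical value is 2.002:

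| p | \|t\| | Observed power, 30 v 30 | Observed power, 15 v 15 (ν = 28) |
|---|---|---|---|
| 0.05 | 2.002 | 0.503 | 0.507 |
| 0.10 | 1.672 | 0.376 | 0.376 |
| 0.20 | 1.296 | 0.247 | 0.245 |
| 0.50 | 0.679 | 0.102 | 0.101 |

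The three-category ANOVA behaves the same way at a different level. With noncentrality 2F and assumed error df of 27 to 87, p = 0.05 gives about 58% and p = 0.20 about 33–34%. For a given test and n, observed power is p on another scale.

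**3. What that figure misses.** Take 30 v 30 and p = 0.20, where observed power is 0.247 at any SD. The standard error is SD × √(2/30), the estimate is 1.296 × SE, and the 95% CI is the estimate ± 2.002 × SE.
- Assumed SD 8: SE 2.07, estimate 2.7, CI −1.5 to 6.8 kPa. This excludes 12.
- Assumed SD 25: SE 6.45, estimate 8.4, CI −4.6 to 21.3 kPa. This does not.

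**4. Power at a fixed effect, or the detectable difference.** With 30 v 30 and SD 14.1, the difference detectable with 90% power is 0.8512 × 14.1 = 12.0 kPa whatever was observed. SE = 14.1 × √(2/30) = 3.641 and the half-width is 2.002 × 3.641 = 7.3.
- p = 0.06: estimate 7.0, CI −0.3 to 14.3. This does not exclude 12.
- p = 0.80: estimate 0.9, CI −6.4 to 8.2. This excludes 12.

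The same 12.0 kPa is reported in both cases.

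**5. How far the kPa figures can be trusted.** They illustrate only. At p = 0.30 with 30 v 30 and SD 14.1, the estimate is 3.8 and the CI is −3.5 to 11.1, so 12 is excluded. With the one-sided SD of 15.7 the upper limit is 12.4. With a Tukey multiplier for three categories (2.38, error df 87) at SD 14.1, the interval is −4.9 to 12.5. Either ordinary alternative reverses that example. At SD 10 the upper limit is 7.9; at SD 18 it is 14.2. Step 2 depends on none of this beyond two-sided α = 0.05.

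**The case against.** The best defence is that the clause refers to effect sizes, so estimates are within its scope, and an interval could be worked out later from reported means, SDs and group sizes. If power is reported as a detectable difference next to the estimate, the standard error is recoverable: in step 4, 12.0 kPa corresponds to a half-width of 7.3 kPa. This stands in part. It means the plan omits to specify an interval, not that one is unobtainable. It does not remove the point, because the plan commits neither to that form of power nor to reporting the two together. The simple back-calculation also assumes one independent value per woman, whereas "SWE will be used to determine tissue stiffness (kPa) at 10 healthy sites and at each fibroid". Group means and SDs alone do not give a valid interval for such clustered data.

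A reader might infer several stronger things that the documents do not support:
- **That the significance tests are invalid.** The clause governs only how non-significant results are interpreted.
- **That 12 kPa is the yardstick for every contrast.** The sample-size paragraph does not tie it to normal versus degenerative fibroids, and it is a design value, not a clinical margin.
- **That 10 × 3 × 2 = 60 healthy-tissue values per woman enter Objective 3.** The repetitions have another stated purpose, "Three repetitions of each measurement will be performed to satisfy Primary Objective 2", and the second session is likewise for reliability. The clustering that matters here is several sites and fibroids within one woman.
- **That the power check after the first 15 women per group has the same fault.** That check is prospective and is meant to confirm the sample size.

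**Conclusion.** The point holds as a cheap improvement to the analysis plan. For non-significant Objective 3 differences the plan names post-hoc power and no interval. At the observed effect, power repeats the p-value (about 50%, 38%, 25% and 10% for a pairwise contrast at p = 0.05, 0.10, 0.20 and 0.50). At a fixed effect, it does not by itself show which differences the data exclude. The documents do not say which is meant, and the conclusion is the same either way.

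It would go too far to say that the study cannot show what is excluded; the plan does not plan to show it. No size in kPa can be put on the consequence for this study, because the SD, sidedness and multiplicity adjustment are not stated and the illustrations move with them.

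**What to change.** In the Primary Objective 3 paragraph of the Statistical Analysis Plan, replace the post-hoc power clause with:

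> For each Primary Objective 3 comparison, significant or not, the estimated difference in kPa and its 95% confidence interval will be reported, using the same multiplicity adjustment as the post-hoc comparisons and allowing for several sites and fibroids from the same woman (for example a random effect for woman, or a bootstrap by woman if normality fails). Non-significant results will be interpreted from the interval and not from post-hoc power; the 12 kPa design difference will serve as a reference only for the contrast on which the sample size was based.

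The shared adjustment matters: an unadjusted interval could exclude zero for a contrast that is non-significant after adjustment. The power check at 15 per group stays as it is.

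The cost is one replacement passage and minor analysis work. The downside is that some comparisons may be shown openly to be inconclusive.
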